3.2 DRUG ADMINISTRATION

3.2.1 *Pomalidomide*

- 3.2.1.1 Pomalidomide will be dispensed through a qualified healthcare professional (including but not limited to, nurses, pharmacists and physicians). These healthcare professionals will be trained by Celgene in requirements specific to counseling of subjects. Once trained these healthcare staff will counsel subjects prior to medication being dispensed to ensure that the subject has complied with all requirements including use of birth control and pregnancy testing (FCBP) and that the subject understands the risks associated with pomalidomide. This step will be documented with a completed Education and Counseling Guidance Document ([Appendix 2](#)) and no drug will be dispensed until this step occurs. Counseling includes verification with the patient that required pregnancy testing was performed and results were negative. A Pomalidomide Information Sheet ([Appendix 3](#)) will be supplied with each medication dispensed.

Subjects will be counseled regarding pomalidomide risks of fetal exposure, pregnancy testing guidelines and acceptable birth control methods ([Appendix 1](#)) prior to commencement of therapy and at least every 28 days while on therapy. In addition, the

‘Pomalidomide Education and Counseling Guidance Document’ ([Appendix 2](#)) will be completed prior to each dispensing of study drug by a clinical investigator with the subject, and the subject will be provided with a copy of the ‘Pomalidomide Information Sheet for Patients Enrolled in Clinical Research Studies’ ([Appendix 3](#)).

- 3.2.1.2 Pomalidomide will be self-administered on an outpatient basis at the assigned dose once daily. Subjects will be instructed to take pomalidomide at approximately the same time every morning. Subjects should fast (water to drink only) for at least 2 hours prior to taking a dose to at least 30 minutes post-dose of pomalidomide. A light breakfast (such as tea without sugar and dry toast) may be taken in the morning but must be completed at least 2 hours prior to taking a morning dose. Sugary and fatty foods should be avoided prior to taking the medication doses.
- 3.2.1.3 Subjects will keep a daily diary recording pomalidomide administration including the time of administration, and any clinical toxicity or other observations made during the cycle ([Appendix 8](#)). This will be used as only an *aide memoire* for subjects. The clinical research team will maintain the primary source record of events including toxicities.
- 3.2.1.4 Thromboprophylaxis with aspirin 81mg or an acceptable alternative agent will continue throughout therapy (days 1-28 of each cycle), as described in Section [4.1.2](#).
- 3.2.1.5 Treatments and corresponding evaluations may be rescheduled to the closest day possible without constituting a protocol violation (e.g. for Federal holidays or unforeseen circumstances such as travel difficulties, snow closures and the like).
- 3.2.1.6 Only enough pomalidomide for one cycle of therapy will be supplied to the patient each cycle.**
- 3.2.1.7 Pomalidomide capsules should be swallowed whole, and should not be broken, chewed or opened.
- 3.2.1.8 If a dose of pomalidomide is missed, it should be taken as soon as possible on the same day. If it is missed for the entire day, it should not be made up.
- 3.2.1.9 Subjects who take more than the prescribed dose of pomalidomide should be instructed to seek emergency medical care if needed and contact study staff immediately.

3.2.2 Special Handling Instructions

Females of childbearing potential should not handle or administer pomalidomide unless they are wearing gloves.

3.2.3 Record of administration

Accurate records will be kept of all study drug administration (including dispensing and dosing) will be made in the source documents.

3.3 DOSE MODIFICATIONS

All treatment modifications should be discussed with the senior clinical investigators on the study. Dose modification guidelines apply to the Phase 1 and Phase 2 portions of the study as well as the Second Optional Course of Therapy.

For Phase 1: Subjects who are enrolled on the initial (5mg) dose level who experience a DLT *not including a thromboembolic event* that resolves to grade 1 (or the grade they had at entry) *within*

28 days and continue to have KS may be considered for further therapy at the 3mg dose level if they continue to have KS requiring therapy. Response assessment for any such patients is described in Section **10.4**.

Table 1: Dose Modification of Pomalidomide

Event	Action	Resumption of Therapy
Neutropenia. ANC 500 to <1000 cells/mm ³ (CTCAE Grade 3)	*If observed during cycle (day 2 of cycle onward) therapy may continue with additional weekly CBCs. If observed day 1 of new cycle , therapy should be held. Consider G-CSF. (filgrastim) 5mcg/kg/daily SC rounded by $\pm 10\%$ to use the most economical combination of available products (commercial vials contain 300 mcg or 480 mcg). Pegylated filgrastim should not be used. Pomalidomide should not be administered during G-CSF treatment or within 24 hours after a G-CSF dose.	CBCs should be evaluated weekly and a new cycle of treatment may commence at the same dose level on or after day 29 once ANC ≥ 1000 cells/mm ³ .
Neutropenia. ANC <500 cells/mm ³ . (CTCAE Grade 4)	*Suspend or hold pomalidomide. Administer G-CSF (filgrastim) 5mcg/kg/daily SC rounded by $\pm 10\%$ to use the most economical combination of available products (commercial vials contain 300 mcg or 480 mcg). Pegylated filgrastim should not be used. Pomalidomide should not be administered during G-CSF treatment or within 24 hours after a G-CSF dose.	CBCs should be evaluated weekly and a new cycle of treatment may commence at the same dose level on or after day 29 once ANC ≥ 1000 cells/mm ³ so long as criteria for a DLT are not met.

Event	Action	Resumption of Therapy
Febrile Neutropenia. ANC <1000 cells/mm ³ with a single temperature >38.3°C or T≥38°C for more than one hour.	Suspend or hold pomalidomide. Supportive care including intravenous antibiotics as outlined in Section 4.2.2. Administer G-CSF (filgrastim) 5mcg/kg/daily SC rounded by ±10% to use the most economical combination of available products (commercial vials contain 300 mcg or 480 mcg). Pegylated filgrastim should not be used. Pomalidomide should not be administered during G-CSF treatment or within 24 hours after a G-CSF dose.	CBCs should be evaluated weekly and a new cycle of treatment may commence at the same dose level on or after day 29 once ANC ≥1000 cells/mm ³ so long as criteria for a DLT are not met.
Thrombocytopenia.: platelet count 25,000 to <50,000 cells/mm ³ . (CTCAE Grade 3)	If observed during cycle (day 2 of cycle onward), pomalidomide may continue with additional weekly CBCs. If observed day 1 of new cycle , pomalidomide should be held. Hold thromboprophylaxis until platelet count ≥ 50000 cells/mm ³ .	CBCs should be evaluated weekly and a new cycle of treatment may commence at the same dose level on or after day 29, once platelet count ≥ 50000 cells/mm ³ so long as criteria for a DLT are not met.
Thrombocytopenia: platelet count < 25,000 cells/mm ³ (CTCAE Grade 4)	Discontinue therapy. Consider platelet transfusion if Plt ≤10000 cells/mm ³ , bleeding or risk factors for bleeding present as outlined in Section 4.2.4. Hold thromboprophylaxis until platelet count ≥ 50,000 cells/mm ³ .	Not to resume
Anemia. Hb <8.0 g/dL (CTCAE Grade 3)	Consider red cell transfusion if symptomatic, or as required to maintain Hb ≥10.0g/L during therapy.	Pomalidomide may continue at the same dose level once Hb ≥10.0g/L so long as criteria for a DLT are not met.

Event	Action	Resumption of Therapy
Thromboembolic events (first episode of superficial venous thrombosis)	Suspend or hold pomalidomide.	On or after day 29 and following documentation of complete resolution (e.g. by ultrasonography) at the same dose level.
Thromboembolic events (Arterial, deep venous, or second episode of superficial venous thrombosis)	Discontinue therapy.	Not to resume.
Infection at any site (\geq CTCAE Grade 3) at least possibly attributable to pomalidomide	Suspend or hold Pomalidomide.	On or after day 29 and following documentation of resolution to \leq CTCAE Grade 1 at the same dose level. Therapy may resume during oral antibiotic consolidation therapy if there is no clinical or laboratory evidence of active infection.
CK elevation at least possibly attributable to pomalidomide (\geq CTCAE Grade 3)	Hold pomalidomide for a maximum of 2 weeks. Encourage increased oral fluid intake and avoidance of strenuous physical activities. Administer intravenous fluid if CK $>10,000$ U/L.	Resume therapy at the same dose level once resolution to \leq CTCAE Grade 2. Permanently discontinue if not at \leq CTCAE Grade 2 after a total of 3 weeks off drug (including the time off drug during the last week of the cycle) or if CK rises again to grade 4 and it is not possibly attributable to excess exercise or to trauma.
Any other DLT of CTCAE Grade 3 at least possibly attributable to pomalidomide	Suspend or hold pomalidomide.	On or after day 29 and following resolution to \leq CTCAE Grade 1 at the same dose level (see Section 3.5).

Event	Action	Resumption of Therapy
Any other DLT of CTCAE Grade 4 at least possibly attributable to pomalidomide	Discontinue therapy.	Not to resume (see section 3.3).

*At the discretion of the investigators, subjects who experience grade 3 or 4 neutropenia requiring G-CSF during a cycle as described below may receive G-CSF 5mcg/kg/daily SC rounded by $\pm 10\%$ to use the most economical combination of available products during the 'rest' days of subsequent cycles to minimize recurrent neutropenia.

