3.5 COST AND COMPENSATION

3.5.1 *Costs*

NIH does not bill health insurance companies or participants for any research or related clinical care that participants receive at the NIH Clinical Center. If some tests and procedures performed outside the NIH Clinical Center, participants may have to pay for these costs if they are not covered by insurance company. Medicines that are not part of the study treatment will not generally be provided or paid for by the NIH Clinical Center.

3.5.2 *Compensation*

Participants will not be compensated on this study.

3.5.3 *Reimbursement*

The NCI will cover the costs of some expenses associated with protocol participation. Some of these costs may be paid directly by the NIH and some may be reimbursed to the participant/guardian as appropriate. The amount and form of these payments are determined by the NCI Travel and Lodging Reimbursement Policy.

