3.6 CRITERIA FOR REMOVAL FROM PROTOCOL THERAPY AND OFF STUDY CRITERIA

Prior to removal from study, effort must be made to have all subjects complete a safety visit approximately 28 days (± 7 days) following the last dose of therapy.

3.6.1 *Off-Therapy*

- 3.6.1.1 Any toxicity which is grade 4 and a dose limiting toxicity as defined in Section [3.1.2](#) at least possibly related to pomalidomide.
- 3.6.1.2 Any toxicity which is grade 3 and a dose limiting toxicity as defined in Section [3.1.2](#) at least possibly related to pomalidomide that does not resolve within 28 days to either grade 1 or the grade the patient had at entry.

- 3.6.1.3 Development of deep venous or arterial thrombosis, whether symptomatic or not, or development of a second on-study superficial venous thrombosis.
- 3.6.1.4 Pregnancy.
- 3.6.1.5 Achievement of pathologically confirmed complete remission.
- 3.6.1.6 Completion of six cycles of therapy (unless continuing to derive clinical benefit, as described in Section 3.1.4, in which case up to 12 cycles may be administered).
- 3.6.1.7 Clinically significant progressive disease compared with the tumor baseline for the current course of therapy by NCI-HAMB modified ACTG KS response criteria, sustained for eight weeks and not attributed to immune reconstitution syndrome. As KS may wax and wane, and improvements may be seen despite an initial period of progression, physician investigators may continue therapy through the first 6 cycles, despite meeting formal criteria for progressive disease, as long as disease progression is not clinically significant. Such cases must be discussed with the Principal Investigator and study subject. Clinically significant progression includes all symptomatic visceral disease and disease which is organ- or life-threatening.
- 3.6.1.8 ECOG performance status ≥ 3 .
- 3.6.1.9 Significant non-adherence to protocol therapy or HAART (the latter only in subjects with HIV-associated KS).
- 3.6.1.10 Inability to achieve HIV viral control, defined as failure to maintain an HIV VL $<10,000$ copies/mL persisting on at least two successive determinations at least four weeks apart and persisting despite optimization of HAART regimen. If a change in HAART regimen is required, a further period of up to eight weeks to assess the effect of this change on HIV VL is allowable.
- 3.6.1.11 Subject requests to be withdrawn from active therapy

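### Table 1's infection row lets a patient resume at the same dose after a grade 4 drug-related infection that, as a DLT, ends therapy under Section 3.6.1.1

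*Combined protocol and SAP*

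**What the plan says.** Section 3.3 applies its dose modification rules to Phase 1, Phase 2 and the optional second course. Three rows of Table 1 matter here.

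- **Infection, grade 3 and above, at least possibly drug-related.** Suspend or hold, then resume at the same dose "On or after day 29 and following documentation of resolution to" grade 1 or below. The row mentions neither grade 4 nor DLT status.
- **CK elevation, grade 3 and above, at least possibly drug-related.** Resume at the same dose once CK is back to grade 2 or below. Stop permanently if that has not happened after 3 weeks off drug, "or if CK rises again to grade 4 and it is not possibly attributable to excess exercise or to trauma".
- **The general stop row.** "Any other DLT of CTCAE Grade 4 at least possibly attributable to pomalidomide" leads to discontinuation.

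Section 3.6.1.1 lists among the off-therapy criteria "Any toxicity which is grade 4 and a dose limiting toxicity as defined in Section" 3.1.2, where the link to pomalidomide is at least possible. Section 3.6.1.2 treats grade 3 DLTs differently: therapy ends only for one "that does not resolve within 28 days to either grade 1 or the grade the patient had at entry".

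Section 3.1.2.1 defines the grade 4 DLTs. Its list of excluded toxicities does not include infection. Section 3.1.2 offers the definition both for judging the toxic dose and as a basis for discussing off-study criteria, but describes DLT assessment as covering the first 8 weeks (2 cycles).

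**The concern.** After a grade 4, possibly drug-related infection, an investigator working from Table 1 would wait for recovery and restart at the same dose. One working from Section 3.6.1.1 would stop for good. The table is what a clinician is likely to consult at that moment, and its row gives no sign that another section removes the patient.

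The event is not far-fetched. Section 1.2.3.4 reports neutropenia as the leading toxicity of the drug. It also describes a fatal infection at 3 mg daily in a solid-tumor study, before that study limited performance status. That study dosed continuously, so no rate carries over to this trial.

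**Working it through.** There is no figure to recompute. The check follows each kind of event through the DLT definition (3.1.2), the off-therapy rule (3.6.1) and Table 1.

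1. **Grade 4 infection, possibly drug-related, not put down to HIV, HIV treatment or KS.** Section 3.1.2.1: a DLT. Section 3.6.1.1: off therapy. Table 1 infection row: hold, then same dose. The general stop row does not clearly reach it, because that row covers other DLTs and infection has its own row. *Direct conflict.*
2. **Grade 4 infection, possibly drug-related but also attributed to HIV, HIV treatment or KS.** Not a DLT, so 3.6.1.1 does not apply. Table 1: hold, then same dose. *No conflict*, and this row is the only rule the event has.
3. **Grade 3 infection, possibly drug-related and not otherwise attributed.** A DLT under 3.1.2.3. Section 3.6.1.2 permits resumption if it resolves within 28 days. Table 1 also permits resumption. *No conflict with 3.6.1.1.*
4. **First grade 4 CK rise with no possible exercise or trauma cause.** Section 3.1.2.2.5 exempts grade 4 CK from DLT status only where exercise or trauma may explain it, so by implication this one is a DLT and 3.6.1.1 ends therapy. Table 1 stops only for a repeat rise to grade 4 or slow recovery. *Conflict by implication.*
5. **Grade 4 CK possibly due to exercise or trauma.** Not a DLT. *No conflict.*

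**Rows affected.** Table 1 has 12 rows: neutropenia (2), febrile neutropenia (1), thrombocytopenia (2), anemia (1), thromboembolism (2), infection (1), CK (1), other DLTs (2); 2+1+2+1+2+1+1+2 = 12. Infection and CK are the only two labelled grade 3 and above. Four rows (grade 4 neutropenia, febrile neutropenia, grade 3 thrombocytopenia, anemia) make resumption conditional on no DLT. Infection and CK have no such condition.

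**Time.** A first course can run 24 + 24 = 48 weeks, or 12 cycles. The DLT window is 8 weeks, or 2 cycles. If 3.6.1.1 inherits that window, the conflict in a full first course is confined to 2 of 12 cycles. If it does not, the conflict runs throughout.

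**Cross-references.** The grade 3 row for other DLTs ends "at the same dose level (see Section 3.5", but that section is "3.5 COST AND COMPENSATION". The grade 4 row ends "Not to resume (see section 3.3", the section that holds the table. Neither leads to 3.6.

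**The case against.** The strongest reply is that the sections can be read together. Section 3.1.4 continues therapy only while no off-therapy criterion is met, 3.1.6.5 carries those criteria into the second course, and 3.3 calls its rules guidelines. On that reading a patient who meets 3.6.1.1 has no dose left to modify. This is probably what was meant, but no text states the precedence, and the row still gives the wrong instruction for this event.

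Safeguards also count. The row requires a hold, a wait to day 29 or later, and documented recovery. Section 3.3 asks for discussion with senior investigators, 7.4.1 has the team review each participant weekly, and 3.6.1.12 lets the principal investigator stop therapy. These lower the risk without saying which instruction applies.

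Three stronger readings are tempting and are not supported:

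- **That the CK row is equally wrong.** A reader might infer this from its matching grade label. But the DLT status of an unexplained grade 4 CK rise is itself an inference, and the row's detailed stop for a repeat rise may mean that one re-challenge was intended.
- **That Phase 1 is compromised.** The Phase 1 paragraph in 3.3 allows 3 mg after a resolved non-thromboembolic DLT, with no grade limit. Section 3.1.5 reports that the first six patients completed 8 weeks without a DLT, so that route is moot. Section 10.4 only says how de-escalated patients are classified for response.
- **That both cross-references are wrong.** The pointer to 3.3 may sensibly mean the opening paragraph there on therapy after a DLT. Only the pointer to 3.5 is clearly misdirected.

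**Conclusion.** The infection row conflicts with Section 3.6.1.1 and should be corrected. It is one row of 12, and one event has two outcomes: same dose, or stop. The CK row is a possible second case.

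The conclusion covers only grade 4 infections that meet 3.1.2.1. It is certain in the first 8 weeks. A reader might infer that it holds for the whole of both courses, up to 96 weeks, but that assumes 3.6.1.1 uses the DLT definitions without their window. Section 3.1.2 points both ways: it offers the definitions for off-study discussion and also ties assessment to 8 weeks.

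Exposure is limited. At amendment G, Section 10.4 foresaw up to 3 further subjects in each cohort. The Phase 1 dose decision, the sample size and the response thresholds do not depend on this point.

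**What to change.** - **Infection row.** Keep it at grade 3 and above, and add that a grade 4 infection meeting 3.1.2.1 is discontinued and not resumed (3.6.1.1). Narrowing the row to grade 3 would leave grade 4 infections that are not DLTs with no rule. Borrowing the no-DLT condition from other rows would also be wrong, because it would block grade 3 infections that 3.6.1.2 allows to resume.
- **Section 3.3.** State that the off-therapy criteria in 3.6.1 take precedence over Table 1.
- **Section 3.6.1.1.** State that the DLT definitions in 3.1.2 apply throughout both courses.
- **CK.** Either stop at a first grade 4 DLT or, if re-challenge is intended, exempt it explicitly in 3.6.1.1.
- **Cross-reference.** Change the pointer to 3.5 in the grade 3 row for other DLTs to 3.6.

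The Phase 1 3 mg paragraph, Section 10.4 and the pointer to 3.3 need no change for this purpose.

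The cost is a short clarifying amendment. The clinical downside is that a patient who recovers from a grade 4 drug-related infection DLT loses the option to resume.

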3.4 STUDY CALENDAR

3.4.1 Initial Treatment Course Calendar

Evaluation	Screen	Pre Therapy ¹	First Cycle		Second and Third Cycles		Fourth and Later Cycles	Post Therapy	
			Day 1	Day 15	Day 1	Day 15		Day 1	Day 29 Final Cycle
History and physical ²	X		X	X	X		X	X	X
Clinical Labs ³	X		X	X	X	X	X	X	X
Pregnancy Test ⁴	X		X	X	X		X	X	X
Pomalidomide Education and Counseling ⁵		X	X		X		X		
HIV Western blot	X								
Chest X-ray	X								
Electrocardiogram	X								
KS Response Evaluation									
KS Tumor Measurements		X			X		X	X	
KS Tumor Photography ⁶		X			X		X	X	
KS Non-invasive Tumor Imaging ⁶		X			X		X	X	
Tumor Biopsies ⁷	X				X			X	
Quality of Life Assessment ⁸		X					X		X
Pharmacokinetics ⁹			X	X					
Adverse Event Monitoring			X						X
KSHV VL (PBMCs and saliva), viral IL-6, human cytokines ¹⁰			X		X		X	X	
KSHV Immune Response Assays ¹¹		X							X
Monocyte and T cell activation and subsets ¹¹		X					X		X
HIV VL (Single Copy Research Assay) ¹²		X	X		X		X	X	X

¹ Pre-therapy studies will be performed after screening and enrollment, and at least 48 hours before commencement of therapy.

² Includes current medications and ECOG performance status

³ See Section 2.2.2 for screening labs, 3.4.3 for baseline labs, 3.4.4 for on treatment labs and 3.4.5 for post treatment labs. Note as described in Section 3.4.4, day 8, 15 and 22 of cycle 1 and Day 15 of cycles 2 and 3 are limited laboratory toxicity checks only. Laboratory toxicity checks may be performed by the patient's primary care physician through a certified outside laboratory with results to be provided to NCI investigators, for patients living at a distance from the Clinical Center.

⁴ In females of child-bearing potential (FCBP), as defined in [Appendix 1](#). Urine and serum β -HCG will be performed within 14 days prior to starting pomalidomide, again within 24 hours of starting pomalidomide, and then performed weekly for the first 28 days of study participation and then every 28 days while on study, at study drug discontinuation, and at day 28 following study drug discontinuation. If menstrual cycles are irregular, the pregnancy testing must occur weekly for the first 28 days and then every 14 days while on study, at study discontinuation, and at days 14 and 28 following study drug discontinuation.

⁵ All patients must be counseled about pregnancy precautions, risks of fetal exposure and other risks. The counseling must be done on Day 1 of each cycle (or at a minimum of every 28 days) and at drug discontinuation. See [Appendix 1](#): Pomalidomide Risks of Fetal Exposure, Pregnancy Testing Guidelines and Acceptable Birth Control Methods and: [Appendix 2](#) Pomalidomide Education and Counseling Guidance Document.

⁶ Pre-therapy, day one of subsequent cycles until the sixth cycle and then (for patients receiving more than six cycles) day one of odd-numbered cycles (beginning with Cycle 7) and again at the end of first course of therapy.

⁷ Pathological confirmation of diagnosis in Department of Pathology, Clinical Center, National Institutes of Health is required for eligibility screening, and may be undertaken using a recent biopsy from an outside institution if available. In this case, an additional research biopsy at baseline is optional. Research biopsy day one of cycle three (only) is optional. Diagnostic and research biopsy at end of first course of therapy is optional. Optional on-therapy research biopsies will not be performed for subjects receiving a second course of therapy.

⁸ Pre-therapy, day one of cycle four, and end of first course of therapy.

⁹ See Section 5.1.1.2 for full pharmacokinetic studies schedule. Not to be performed for subjects receiving a second course of therapy.

¹⁰ At each collection: 1 yellow top tube for PBMCs; 1 blue top tube for saliva; 2 red top tubes for viral IL-6; 3 green top tubes for cytokines; 2 yellow top tubes for storage

¹¹ Repeated day one of cycle four and 28±7 days following the end of the first course of therapy

¹² Only in HIV infected subjects whose HIV VL is undetectable by conventional assays.

As noted in Section 3.2.1.5, with the exception of pharmacokinetics, treatments and corresponding evaluations may be rescheduled to the closest day possible without constituting a protocol violation (e.g. for Federal holidays or unforeseen circumstances such as travel difficulties, snow closures and the like).

